4.2.3. Duration of Response

Some duration (months) of responses are defined as follows:

- Duration of CR (DOCR) is defined as the time from the first occurrence of CR until disease progression, relapse, or death due to any cause, whichever comes first. Only patients with CR will be included in this analysis.
- Duration of CRh (DOCRh) is defined as the time from the first occurrence of CRh until disease progression, relapse, or death due to any cause, whichever comes first. Only patients with CRh will be included in this analysis.
- Duration of cCR-1 (DOcCR1) is defined as the time from the first occurrence of cCR-1 until disease progression, relapse, or death due to any cause, whichever comes first. Only patients with cCR-1 will be included in this analysis.
- Duration of cCR-2 (DOcCR2) is defined as the time from the first occurrence of cCR-2 until disease progression, relapse, or death due to any cause, whichever comes first. Only patients with cCR-2 will be included in this analysis.
- Duration of cCR-3 (DOcCR3) is defined as the time from the first occurrence of cCR-3 until disease progression, relapse, or death due to any cause, whichever comes first. Only patients with cCR-3 will be included in this analysis.
- Duration of objective response (DOOR) is defined as the time from the first occurrence of objective response (CR_{MRD}-, CR, CRh, CRi, MLFS, or PR) until disease progression, relapse, or death due to any cause, whichever comes first. Only patients with objective response will be included in this analysis.

The duration (months) of response is generally calculated as (date of death or PD or Relapse or last assessment – date of first occurrence of interested response category + 1)/30.4375. The rule of censoring will follow these rules outlined in [Table 2](#).

Table 2 Outcome and Event or Censoring Dates for Duration of Response

Rule	Situation	Date of Event or Censoring	Outcome
1	Relapse (or PD) documented between schedule tumor assessment visits or after one missing tumor assessment visit	Date of first documented relapse (or PD)	Event
2	Death without relapse (or PD) between scheduled assessment visit or death after one missing tumor assessment visit	Date of death	Event

4	No death or relapse (or PD) by the time of data cut-off for final analysis	Date of last adequate tumor assessment prior to or on analysis data cutoff date	Censored
5	Early discontinuation (lost to follow-up or withdrawal of consent) of study without death or relapse (or PD)	Date of last adequate tumor assessment	Censored
6	Subsequent anti-tumor therapy started prior to relapse (or PD) or death	Date of last adequate assessment prior to or on date of initiation of subsequent anti-tumor therapy	Censored
7	Death or relapse (or PD) after two or more consecutive missed or inadequate tumor assessment visits	Date of last adequate tumor assessment prior to missed visits	Censored

PD is only applicable for the duration of objective response.

Note: An adequate tumor assessment is defined as an assessment where the Investigator determined response is CR_{MRD}-, CR, CRh, CRI, MLFS, PR, SD, and PD. If PD and subsequent anti-cancer therapy occur on the same day, will assume that the progression was documented first, e.g. outcome is progression and the date is the date of the assessment of progression.

(a) Determination of one missing or inadequate assessment

The following provides the rules for determining whether one tumor assessments is missed, of note, the relative day in the rules refers to the first dose date of study drug from Cycle 1 in continuous cycle.

- If the tumor assessment date is prior to day 1 of week 23 (relative day $< (24 - 1) \times 7 + 1 = 162$), and the difference between the tumor assessment date and the next adjacent adequate tumor assessment ≥ 63 days (8 weeks * 7 + 7), then the tumor assessment is considered as occurring after one missing tumor assessment;
- If the tumor assessment date is on or after day 1 of week 23 (relative day $< (24 - 1) \times 7 + 1 = 162$), and the difference between the tumor assessment date and the next adjacent adequate tumor assessment ≥ 98 days (12 weeks * 7 + 14), then the tumor assessment is considered as occurring after one missing tumor assessment.

(b) Determination of two or more consecutive missing or inadequate assessments

The following provides the rules for determining whether two or more consecutive tumor assessments are missed.

- If the tumor assessment date is prior to day 1 of week 15 (relative day $< (16 - 1) \times 7 + 1 = 106$), and the difference between the tumor assessment date and the next adjacent adequate tumor assessment ≥ 126 days ($= 2 * (8 \text{ weeks} * 7 + 7)$), then the tumor assessment is considered as occurring after two or more consecutive missing tumor assessments;
- If the tumor assessment date is between day 1 of week 15 and day 1 of week 23 (relative day between $(16 - 1) \times 7 + 1 = 106$ and $(24 - 1) \times 7 + 1 = 162$), and the difference between the tumor assessment date and the next adjacent adequate tumor assessment ≥ 161 days ($= (8 \text{ weeks} * 7 + 7) + 12 \text{ weeks} * 7 + 2 \text{ weeks} * 7$)), then the tumor assessment is considered as occurring after two or more consecutive missing tumor assessments;

- If the tumor assessment date is on or after day 1 of week 23 (relative day $\geq (24 - 1) \times 7 + 1 = 162$), and the difference between the tumor assessment date and the next adjacent adequate tumor assessment ≥ 196 days ($= 2 * (12 \text{ weeks} * 7 + 2 \text{ weeks} * 7)$), then the tumor assessment is considered as occurring after two or more consecutive missing tumor assessments.

Reasons for censoring are included in Table 3 following the hierarchy.

Table 3 Duration of Response Censoring Reasons and Hierarchy

Hierarchy	Condition	Censoring Reason
1	Subsequent anti-tumor therapy started prior to relapse (or PD) or death	Subsequent anti-tumor therapy started prior to relapse (or PD) or death
2	Death or relapse (or PD) after two or more consecutive missed or inadequate tumor assessment visits	Missed or inadequate two or more consecutive tumor assessment visits
3	Drops out before end of study, no relapse (or PD) or death, lost to follow-up	No death or relapse (or PD), lost to follow-up
4	Drops out before end of study no relapse (or PD) or death, withdrawal by subject from the study	No death or relapse (or PD), withdrawal by subject
5	No death or relapse (or PD) by the time of data cut-off for the analysis	No death or relapse (or PD) by the time of data cut-off for the analysis

PD is only applicable for the duration of objective response.

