APPENDIX 8 2017 EUROPEAN LEUKEMIANET EFFICACY CRITERIA FOR AML

Treatment Response	Efficacy Criteria
Complete response (CR)	
 • Myeloblast percentage <5% • Blast cells without Auer bodies • No blast cells in peripheral blood • No extramedullary lesion • ANC $\geq 1.0 \times 10^9/L$, PLT $\geq 100 \times 10^9/L$
Complete response with negative minimal residual disease (CR _{MRD})	
 • CR with negative RT-qPCR or CR with negative MFC
Complete response with incomplete count recovery (CRI)	
 • Meets all other criteria of CR but ANC $< 1.0 \times 10^9/L$ or PLT $< 100 \times 10^9/L$
Morphologically leukemia-free status (MLFS) ^a	
 • Myeloblast percentage <5% • Blast cells without Auer bodies • No extramedullary lesion • No hematological recovery requirements
Partial response (PR)	
 • Meets all hematological criteria for CR • The percentage of myeloblasts decreases from baseline by least 50% and reaches 5% to 25%
Stable disease (SD) ^b	
 • Fails to meet criteria for CR, CRI, CR_{MRD}, MLFS, PR, or progressive disease
Progressive disease ^{c, d}	
 • Increase in bone marrow blast percentage and/or absolute peripheral blood blast cells 
 – The percentage of myeloblasts increases from baseline by >50% (if blast cells at baseline are <30%, net increased value needs to be $\geq 15\%$); or percentage of myeloblasts >70% continues for at least 3 months; ANC is not seen to be improved by at least 100%, reaching ($>0.5 \times 10^9/L$ and/or PLT reaches $>50 \times 10^9/L$, without blood transfusion); or – The absolute peripheral blood blast cell count (WBC \times blast cell ratio) increases by >50% and reaches $>25 \times 10^9/L$ (without differentiation syndrome); or • New extramedullary diseases • After achieving CR/CR_{MRD}/CRI, $\geq 5\%$ of the blast cells recur in the bone marrow; or • Blast cells occur in the peripheral blood; or • Extramedullary lesions occur
Hematologic recurrence	

AML=acute myeloid leukemia; ANC=absolute neutrophil count; CR=complete response; MFC=multiparameter flow cytometry; PLT=platelet; RT-qPCR=quantitative reverse transcription polymerase chain reaction; WBC=white blood cell.

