6	CR by 24 weeks ^a then start subsequent anticancer therapy (prior to death or relapse or no relapse)	Date of the last adequate disease assessment documenting no relapse prior to start of subsequent anticancer therapy or missed response assessments	Censored
7	CR by 24 weeks ^a then death or relapse after missed or inadequate two or more consecutive tumor assessments		Censored
8	CR by 24 weeks ^a and neither relapse nor death		Censored
9	No baseline or post-baseline adequate disease assessment	Date of first administration of study treatment	Censored

CR: including CRMRD-, CR, CRh and CRi; EFS = event-free survival; TF = treatment failure.

^aBased on the protocol schedule of assessments, “+1 week window” is allowed.

Note: The same algorithm for determination of one and two/more consecutive missing or inadequate assessments can be found in [Section 4.2.3..](#)

Reasons for censoring are included in [Table 5](#) following the hierarchy.

Table 5 EFS Censoring Reasons and Hierarchy

Hierarchy	Condition	Censoring Reason
1	No baseline or post-baseline adequate disease assessment	No baseline or post-baseline tumor assessments
2	On treatment $<$ 24 weeks without CR and active in study	On treatment $<$ 24 weeks, active in study
3	CR by 24 weeks then start subsequent anticancer therapy	CR by 24 weeks, start subsequent anticancer therapy
4	CR by 24 weeks then death or relapse after missed or inadequate two or more consecutive tumor assessments	CR by 24 weeks, missed or inadequate two or more consecutive tumor assessments
5	CR by 24 weeks, no relapse or death, lost to follow-up	CR by 24 weeks, lost to follow-up

6	CR by 24 weeks, no relapse or death, withdrawal by subject from the study	CR by 24 weeks, withdrawal by subject
7	CR by 24 weeks, no relapse or death, ongoing in study	CR by 24 weeks, ongoing without relapse or death

CR: including CRMRD-, CR, CRh and CRi; EFS = event-free survival.

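### SAP 4.2.3 contradicts itself on whether PD ends a complete response, so a loss of CR recorded only as PD can be censored instead of counted

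*SAP*

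**What the plan says.** SAP 4.2.3 defines five CR-based durations in the same form. For DOCR the period runs "from the first occurrence of CR until disease progression, relapse, or death due to any cause", and for DOcCR1 it runs "from the first occurrence of cCR-1 until disease progression, relapse, or death due to any cause". DOCRh, DOcCR2 and DOcCR3 follow the same pattern. The formula shared by all duration endpoints takes as its end point the "date of death or PD or Relapse or last assessment", with no restriction by endpoint.

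The section then refers to Table 2 for censoring. The footnote to Table 2 states that "PD is only applicable for the duration of objective response", and the same sentence stands under Table 3, which lists the censoring reasons. The Table 2 note on adequate assessments lists response categories from CR_MRD- down to PD, with no relapse category. The matching PFS note in SAP 4.2.7 ends its list with PD and relapse together.

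Protocol Appendix 8 has separate entries for progressive disease and hematologic recurrence. Progressive disease includes "New extramedullary diseases". Recurrence, which is conditional on a prior CR, CR_MRD or CRi, includes "Extramedullary lesions occur".

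**The concern.** The definitions and the operative table give opposite instructions for one kind of record: a patient in a CR-type response whose loss of response is entered as PD. Under the definitions this is an event at the date of the visit. Under the footnote it is not an event, and the patient passes to the censoring rules.

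A loss of remission treated as a censored observation lengthens the estimated duration of response. DOcCR1 carries extra weight here: SAP section 7 drops disease-free survival and time to hematologic recurrence on the ground that DOcCR1 has the same or a similar rationale. The PD exclusion itself is not in section 7's list of changes from the protocol.

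**Working it through.** The documents attach no event count or precision figure to the duration endpoints, so there is no stated number to reproduce. The check is a reading of the rules, followed by a hypothetical illustration.

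**Step 1: apply the footnote literally.** For DOCR, DOCRh and DOcCR1 to DOcCR3, the bracketed PD drops out of every Table 2 rule. A patient with CR, then PD, then no recorded relapse is handled as follows:

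- Rule 1 (documented relapse): no event.
- Rule 4 (no relapse or death by cut-off) or Rule 5 (lost to follow-up or consent withdrawn): censored at the last adequate assessment.
- Rule 6 (new anti-tumor therapy before relapse or death): censored at the last adequate assessment on or before the start of that therapy.
- Rule 2 (death without relapse): an event, but at the later death date.
- Rule 7 (death after two or more missed assessments): censored.

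PD is on the list of adequate assessments, so the censoring date can be the PD visit itself. The recorded time is then unchanged, but the event indicator is reversed.

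**Step 2: ask whether the labels can diverge.** In Appendix 8, each PD criterion reached after a CR also meets a recurrence criterion:

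- A marrow blast rise large enough for PD exceeds the 5% recurrence threshold.
- A peripheral blast rise large enough for PD means that blasts are present in blood.
- New extramedullary disease appears under both entries.

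Recurrence is therefore always available as the correct label. The documents do not make it the only possible record. There is no precedence rule in Appendix 8, no relapse category in the Table 2 scale, and no SAP rule mapping PD after CR to relapse. The recurrence entry also does not name CRh, which SAP 4.2.1 has the medical team derive outside the investigator's assessment.

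**Step 3: hypothetical size.** Assume five CR responders who lose response at 3, 5, 6, 9 and 12 months.

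- All counted: S(3) = 0.8, S(5) = 0.6, S(6) = 0.4. The median is 6 months.
- Loss at 5 months censored: S(3) = 0.8, S(6) = 0.8 × 2/3 = 0.533, S(9) = 0.533 × 1/2 = 0.267. The median is 9 months.
- Losses at 5 and 9 months censored: S(3) = 0.8, S(6) = 0.533, S(12) = 0. The median is 12 months.
- Loss at 9 months only censored: S(6) is still 0.4. The median stays at 6 months.

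In a large sample, assume exponential durations with a true median of 6 months, and let a fraction f of losses be labelled PD at random and censored at that visit. The event hazard falls by the factor (1 − f), so the Kaplan-Meier median tends to 6/(1 − f): 6.7 months at f = 10%, 8.0 at 25%, 12.0 at 50% and 24.0 at 75%. A simulation of 100,000 durations gave 6.65, 7.98, 12.01 and 23.65. The documents give no value for f.

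**The case against.** The strongest reply is that the footnote is deliberate and harmless. Protocol 9.2.7.1 defines disease-free survival as relapse or death, without PD, and SAP section 7 treats DOcCR1 as its equivalent. That fits the footnote better than the definition. Appendix 8 calls loss of CR recurrence, so an investigator who follows it records a relapse and Rule 1 counts it. On this view the loose text is the definition, and no patient is affected.

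Much of this stands. The footnote appears twice and looks intended, and the effect arises only if PD alone is recorded. It does not remove the contradiction, and nothing in the SAP ensures the relapse label.

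A reader might also infer several stronger things that the documents do not support:

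- **That the event is lost from every endpoint.** It is not. Duration of objective response (DOOR) includes all CR-type responders and keeps PD as an event, and PFS (Table 7) counts PD or relapse, both subject to their usual censoring rules. It is only the CR-duration endpoints that miss it.
- **That EFS is contradictory too.** SAP 4.2.5 defines EFS by treatment failure, relapse or death, and Table 4 matches, censoring a patient with CR "and neither relapse nor death". EFS depends on the same label but agrees with its own definition.
- **That every such patient is censored.** A later death can still count under Rule 2, at a later date.
- **That the median would double.** The 6-to-12-month example assumes that two losses in five (40%) are labelled PD, and it depends on which two.

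**Conclusion.** The contradiction within SAP 4.2.3 is certain from the text and sits in an operative event and censoring rule. Its consequence is conditional. If a loss of a CR-type response is recorded as PD only and the footnote governs, DOCR, DOCRh and DOcCR1 to DOcCR3 are overstated. If every such loss is recorded as relapse, nothing changes.

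The size cannot be stated, and the figures above are illustrations on assumed data. No hypothesis is tested, so only estimates are affected. Groups will be small: the planned 24 to 30 evaluable escalation patients over eight dose levels average 3 to 3.75 per level (24/8 and 30/8), and the note to SAP Table 13 says that only one expansion patient was enrolled. Medians will be imprecise on either reading, but a single label can move one.

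**What to change.** Align the definitions, the formula and the two footnotes in SAP 4.2.3 in one of two ways:

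1. Delete both footnotes, so that PD or relapse is an event for all duration endpoints.
2. State that any PD recorded after CR, CR_MRD-, CRh or CRi is analysed as relapse at its documented date.

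The two should give the same event dates, since both count the first PD or relapse recorded after the response. With either choice:

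- Leave the new-therapy and missed-visit censoring in Table 2 Rules 6 and 7 as it is.
- Add relapse to the Table 2 list of adequate assessments, as the PFS note already does.
- For consistency, apply the same mapping of PD to relapse after CR in EFS, with Table 4 Rules 6 and 7 unchanged.

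The cost is SAP wording and the matching program specification. No new data are needed, because PD dates are already used for PFS.

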1.3 Schedule of Events

The Schedules of Events are presented in [Table 1](#) (dose escalation) and [Table 2](#) (dose expansion).

Table 1 Schedule of Events (Dose Escalation)

Cycle/Period	Pre-screening	Screening	PK Week ^a	C1			C2		C3+	EOT	Safety Follow-up	Efficacy Follow-up	Survival Follow-up		
				Single Dose Visit	D1	D8	D15	D22	D1	D15	D1	Within 7 days after last dose	30 days after EOT Visit	Every 12 weeks from EOT Visit	Every 12 weeks from EOT Visit
Visit															
Visit window (days)		-28 to -1	0	0	±1	±1	±1	±1	±1	±1	±3	±3	±7	±14	±14
Activities															
Pre-screening informed consent	X														
Main informed consent ^b		X													
mIDH status ^c		X													
Medical history and demographics ^d	X	X													
Prior and concomitant medications and concomitant procedures ^e		X	X	X	X	X	X	X	X	X	X	X	X	X	
Height ^f		X													
Physical examination, vital signs, and weight ^f		X	X	X	X	X	X	X	X	X	X	X			
ECOG performance status ^f		X	X	X		X			X	X	X	X	X		
Ophthalmologic examination ^g		X							X (±1 week)		Every 12 weeks from C4D1 (±7 days)	X			
Laboratory evaluations: ^f															
Hematology ^h		X	X	X	X	X	X	X	X	X	X	X			
Blood chemistry ⁱ		X	X		X	X	X	X	X	X	X	X			
Blood amylase and lipase			X		X	X	X	X	X	X	X	X	X		
Fasting lipid panel ^j			X						X		X	X	X		
Coagulation indicators ^k			X					X	X	X	X		X		
HbA1C			X						X		X	X	X		
Pregnancy test ^l		X	X	X					X		X	X	X		

Cycle/Period	Pre-screening	Screening	PK Week ^a	C1			C2		C3+	EOT	Safety Follow-up	Efficacy Follow-up	Survival Follow-up
				Single Dose Visit	D1	D8	D15	D22	D1				
Visit			Single Dose Visit							Within 7 days after last dose	30 days after EOT Visit	Every 12 weeks from EOT Visit	Every 12 weeks from EOT Visit
Visit window (days)		-28 to -1	0	0	±1	±1	±1	±1	±1	±3	±3	±7	±14
Activities													
Urinalysis ^m			X						X		X		
Virological screening ⁿ		X											
Blood and/or bone marrow aspiration and/or biopsy ^o				Refer to Appendix 1									
PK and PD assessments				Refer to Appendix 1									
12-lead ECG ^p				Refer to Appendix 1									
ECHO/MUGA scan ^q		X		X					X		Cycle 3 Day 1 then Day 1 of every odd cycle	X	
Tumor evaluation/imaging ^y		X		Every 8 weeks (±7 days) during the first 24 weeks and every 12 weeks (±14 days) thereafter						X		X	
Blood transfusion history ^r		X											
Blood transfusion record ^s			X	X	X	X	X	X	X	X	X	X	
Drug/dispense/return ^v			X	X					X		X		
Study drug administration				Refer to Table 4									

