6.1.14 Efficacy Evaluation

Efficacy evaluation of AML will be performed based on 2017 European LeukemiaNet (ELN) criteria ([Appendix 8](#)). Efficacy evaluation of HR-MDS will be performed based on the International Working Group response criteria in myelodysplasia ([Appendix 12](#)). Efficacy evaluation of AITL will be performed based on Lugano Classification ([Cheson 2014](#)) for Hodgkin and Non-Hodgkin's Lymphoma ([Appendix 9](#)).

Tumor evaluations will be conducted at screening, every 8 weeks (± 7 days) during the first 24 weeks (ie, Day 1 of Cycles 3, 5, and 7), and every 12 weeks (± 14 days) thereafter (ie, Day 1 of Cycles 10, 13, and so on) through EOT, or end of Efficacy Follow-up period (if applicable). Patients who discontinue HMPL-306 treatment due to reasons other than disease progression will continue tumor assessment according to previous tumor evaluation schedule until disease progression, as defined in [Appendix 8](#) and [Appendix 9](#), or start of new antineoplastic therapy (see [Table 1](#)). The same imaging procedure and laboratory tests used to define measurable lesions at baseline should be used throughout the study for each patient.

The baseline tumor assessment should be completed within 28 days prior to the first dose of study treatment (depending on the patient's disease status, a window may be acceptable based on a discussion between the investigator and the sponsor's medical monitor). Tumor assessments completed as standard of care, prior to signing of the informed consent and within 28 days of first dose of study treatment, may be used as baseline assessment.

Response evaluation of patients will be based on the most recent results of physical, bone marrow (if applicable), imaging, and hematological examinations, per local assessment. If a patient needs to delay the study drug after bone marrow examination and wait for recovery of peripheral blood count, then routine blood test results within 2 weeks after bone marrow analysis can be used to determine response.

For patients with myeloid malignancies, this assessment should be done using a blood test, bone marrow aspiration and/or biopsy, and physical examination as per the Schedule of Events (see [Table 1](#)).

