9.1.1 Statistical Hypothesis

No formal hypothesis testing is planned for this study. For efficacy endpoints, the study will provide estimates and associated 95% confidence interval (CI) for precision.

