2.2 Study Design

This is a phase 1, open-label, multicenter, single-arm study to evaluate safety, tolerability, PK, PD and preliminary efficacy of HMPL-306 administered orally in treatment of patients with advanced relapsed, refractory, or resistant hematological malignancies that harbor IDH mutations. The study consists of 2 parts: dose escalation part (Part 1) and dose expansion part (Part 2).

The first part of the study is dose escalation, where cohorts of patients will receive ascending oral doses of HMPL-306 to determine MTD and/or the RP2D. The modified toxicity probability interval-2 (mTPI-2) ([Greenberg 2012](#), [Guo 2017](#)) design will be used to perform dose escalation and MTD/RP2D determination. Briefly, the mTPI-2 method uses a Bayesian framework and a hierarchical model to compute the dose escalation based on the interval between the toxicity rate of each dose level and target probability ([Greenberg 2012](#), [Guo 2017](#)). This study is designed targeting a DLT rate of 20% with an equivalence interval of 15% to 25%.

Seven days prior to initiating daily administration of HMPL-306 from Cycle 1 Day 1 (C1D1), patients enrolled in each cohort during dose escalation will be administered a single oral dose of HMPL-306 on Day -7 relative to C1D1 (Day 1 of PK week). Serial blood samples will be collected from Days 1 to 7 of the PK week for analysis of plasma concentrations of HMPL-306 and 2-HG.

A cycle of study treatment is defined as 28 days of continuous daily dosing. After the PK week, dose escalation will start at **[REDACTED]** mg QD orally (PO) for Cohort 1 and then escalate in the sequence of **[REDACTED]** mg QD, and **[REDACTED]** mg QD.

Safety monitoring and evaluation of dose escalation will be carried out by the Safety Review Committee (SRC), which is comprised of the sponsor and investigators.

[figure not shown]
In the dose-expansion part, 1 cohort of patients will receive HMPL-306 at MTD and/or RP2D to evaluate further the safety, tolerability, PK, PD, and preliminary efficacy in approximately 10 patients with advanced relapsed, refractory, or resistant hematological malignancies with IDH mutations. Patients enrolled in the dose expansion part must not have standard therapeutic options available (including IDH inhibitors where approved) and must have the following:

- Relapsed AML unsuitable for intensive chemotherapy or venetoclax-based regimen or target agents;

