4. ENDPOINTS

4.1. General Principles for Derived and Transformed Data

4.1.1. Reference Start Date and End Date and Study Day

(1) Reference start date

Dose escalation part:

For efficacy analysis, reference start date (Day 1) is defined as the first date when a non-zero dose of study treatment in continuous dosing cycle (i.e. excluding single oral dose from the PK week) is administrated.

For safety analysis, reference start date (Day 1) is defined as the first date when a non-zero dose of study treatment (i.e. including single oral dose from the PK week) is administrated.

Dose expansion part:

Reference start date (Day 1) is defined as the first date when a non-zero dose of study treatment is administrated.

(2) Reference end date

Reference end date is defined as the last date when a non-zero dose of study treatment is administered.

(3) Study day

Study day will be calculated from the reference start date, and it will be used to show start/stop day of assessments or events relative to the start date of study treatment.

- If the date of the event is on or after the reference start date, study day = (date of event – reference start date) + 1.
- If the date of the event is prior to the reference start date, study day = (date of event – reference start date).

Note that, the day of the first dose of study drug is day 1 and the day before it is day – 1, not day 0.

In the situation where the event date is partial or missing, the date will appear partial or missing in the listings.

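### The missed-visit algorithm in SAP 4.2.3 flags the assessment before the gap, gives no gap for deaths and prints inconsistent cut-points, so event or censoring can be coded in more than one way; few patients are affected

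*SAP*

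**What the plan says.** SAP 4.2.3 has two rules. Rule (a) identifies one missed assessment (gap limits 63 and 98 days). Rule (b) identifies two or more (limits ≥ 126, ≥ 161 and ≥ 196 days). The limit depends on the study day of an assessment. The first bullet of rule (b) opens "If the tumor assessment date is prior to day 1 of week 15" and equates that day with Day 106. Bullets in both rules open "If the tumor assessment date is on or after day 1 of week 23" and equate that day with Day 162. Rule (a) prints < 162 beside those words; rule (b) prints ≥ 162.

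Each bullet names an assessment, compares its date with that of the next adequate assessment, and then labels the named assessment as the one that follows the missed visits.

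Table 2 keeps an event after one missed visit, deaths included: "Death without relapse (or PD) between scheduled assessment visit or death after one missing tumor assessment visit". Its rule 7 censors relapse, progression or death after two or more. Table 7 (PFS) and Table 4 (EFS) follow the same pattern and refer back to 4.2.3.

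**The concern.** The named assessment precedes the next one, so it cannot be the one that follows the gap. A programmer must decide which date carries the cut-point and which record is flagged. For deaths there is nothing to code at all: both rules measure only between two tumor assessments, yet Table 2 rule 7 and Table 7 rule 7 need a gap ending in death.

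The conflicting labels, the reversed sign and the ≥ limits add further ambiguity. At stake is whether single events count or are censored in three secondary endpoints. These are summarised by dose level in a study planned at about 40 to 50 patients, so one reclassified event can move a group's Kaplan-Meier estimate.

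**Working it through.** **Inputs.** Day 1 is first dose (SAP 4.1.1: "the day of the first dose of study drug is day 1"); 4.2.3 counts from the first continuous dose of Cycle 1. Cycle length is from SAP 2.2: "A cycle of study treatment is defined as 28 days of continuous daily dosing". Visits are from protocol 6.1.14: "during the first 24 weeks (ie, Day 1 of Cycles 3, 5, and 7), and every 12 weeks", continuing at Cycles 10, 13 and so on. Windows are from protocol 1.3: "Every 8 weeks (±7 days) during the first 24 weeks and every 12 weeks (±14 days) thereafter".

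**The plan's own figures reproduce.** (24−1)×7+1 = 162; (16−1)×7+1 = 106; 56+7 = 63; 84+14 = 98; 2×63 = 126; 63+98 = 161; 2×98 = 196.

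**Visit windows**, with visit day = (cycle−1)×28+1:

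| Visit | Day | Window |
|---|---|---|
| C3 | 57 | 50–64 |
| C5 | 113 | 106–120 |
| C7 | 169 | 162–176 |
| C10 | 253 | 239–267 |
| C13 | 337 | 323–351 |
| C16 | 421 | 407–435 |
| C19 | 505 | 491–519 |

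**1. Which date carries the cut-point.** Take C3, then an event at C10, with C5 and C7 missed.
- There are 15×29 = 435 in-window date pairs, with gaps from 239−64 = 175 to 267−50 = 217 days.
- Read on the earlier date (Days 50–64, before 106), the limit is 126 and all 435 are censored, as Tables 2 and 7 intend.
- Read on the later date (after 162), the limit is 196. Gaps are symmetric about 253−57 = 196, and 15 pairs equal 196 exactly. So (435−15)/2 = 210 pairs, with gaps of 175–195 days, stay events despite two missed visits.
- The other two-missed sequences have smallest gaps of 203 (C5 to C13), 231 (C7 to C16) and 224 days (C10 to C19). All exceed 196, so they are censored on either reading.

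**2. Labels against formulas.** Day 1 of week w is (w−1)×7+1, so week 15 starts on Day 99 and week 23 on Day 155. Days 106 and 162 start weeks 16 and 24. They are also the days the C5 and C7 windows open (113−7 and 169−7), so the formulas look intended. The conflict changes the limit by 35 days (126 or 161; 161 or 196) for assessments on Days 99–105 or 155–161. No scheduled window covers those days.

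**3. Sign.** With < 162, the second bullet of rule (a) has the same condition as the first, and no one-missed rule remains from Day 162 on. Rule (a) separates zero from one missed visit, and Tables 2 and 7 count both as events.

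**4. The ≥ limits, one visit missed:**

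| Sequence | Largest gap | Limit | Pairs censored |
|---|---|---|---|
| C3 to C7 | 176−50 = 126 | 126 | 1 of 225 |
| C5 to C10 | 267−106 = 161 | 161 | 1 of 435 |
| C7 to C13 | 351−162 = 189 | 196 | 0 of 435 |
| C10 to C16 | 435−239 = 196 | 196 | 1 of 841 |

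The nominal gaps (112, 140 and 168 days) stay below the limits. If the difference were counted with +1, as the SAP's durations are, each affected sequence would have 3 pairs. With > and plain subtraction, no one-missed pair is censored. Every two-missed pair still is: 175 > 126, 203 > 161, and 224 and 231 > 196.

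**5. Off-treatment follow-up.** Protocol 6.1.19 and SAP 2.2 put patients who stop drug without progression on 12-weekly assessments counted from end of treatment or the latest assessment. Protocol 6.1.14 instead continues the earlier schedule. Under the 12-weekly interval one missed visit gives 2×84 = 168 days (140–196 with ±14-day windows). That exceeds 126 and 161, the limits in force when the last assessment is before Day 162. Two missed visits give 252 days (224–280).

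**The case against.** The best defence is that most of this is typographical. The formulas give 106 and 162 wherever they are printed, so the numeric rule is consistent and only the week names are wrong. The words beside the reversed sign already give the direction, and rule (b), which does decide censoring, prints ≥ 162 correctly. Reading the cut-point on the earlier date is the only workable reading, and a careful programmer would find it. The study plans no hypothesis tests (protocol 9.1.1: "No formal hypothesis testing is planned for this study"). Duration of response covers responders only, and EFS applies the missed-visit rule only to patients with CR by 24 weeks.

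All of that stands as a limit on size. It does not supply a gap for deaths, and it relies on the programmer overriding text that flags the wrong record.

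A reader might infer that the ≥ limits generally censor events after one missed visit, or that the reversed sign misclassifies events. The documents support neither. The first happens on schedule only when two visits fall at opposite window edges, and the second changes no outcome. Nor would replacing ≥ by > alone restore agreement with Tables 2 and 7, because the off-treatment route in step 5 remains.

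**Conclusion.** The algorithm is wrong as printed and should be corrected, as a minor point. The substantive faults are the flagging of the assessment before the gap and the missing rule for deaths. Reading the cut-point on the wrong date would leave 210 of 435 C3-to-C10 pairs as events after two missed visits. The label conflict reaches only off-window or unscheduled assessments, the sign is a coding ambiguity, and the ≥ limits matter only at exact equality. Few patients are affected.

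This rests on the 28-day cycle calendar and the stated windows. The fractions count possible date pairs; they are not probabilities that a patient is affected. They cover gaps that open at a post-baseline assessment, so a PFS gap that opens at baseline is not counted. The size of the off-treatment route depends on which follow-up schedule applies, which the documents leave open.

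**What to change.** In SAP 4.2.3:
- State the cut-points once, as Days 106 and 162 (day 1 of weeks 16 and 24), read on the last adequate assessment before the gap.
- Measure the gap from that assessment to the later progression or relapse assessment, or to death, as a plain date difference without +1. Flag that later event.
- Correct the sign in the second bullet of rule (a) to ≥ 162.
- In rule (b) use > 126, > 161 and > 196.
- Reconcile protocol 6.1.14 with protocol 6.1.19 and SAP 2.2 on off-treatment assessments. Where the 12-weekly interval applies, use the > 196 limit whatever the study day; one missed visit (at most 196 days) then stays an event and two (at least 224 days) are censored.

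EFS and PFS inherit the change through their cross-references. The cost is SAP wording before database lock, plus the reconciliation of the follow-up sections; no data collection is added.
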